From this model, relevant clinical parameters can be determined, such as: pelvic obliquity, trunk inclination and kyphosis and lordosis angles (Huysmans et al. 2005; Schulte et al 2008; Betsch et al. 2010).

The reliability coefficients of the rasterstereographic assessment method for the study of the sagittal plane were reported as excellent ($ICC > 0.95$) for both intra-examiner (Schroeder et al. 2015) and inter-examiner (Mohokum et al. 2010). Another systematic review (Mohokum et al. 2015) concluded that rasterstereography can be considered valid for both screening and monitoring.

A recent study (Schroeder and Hollander 2018) used rasterstereography (spinometry) to evaluate the immediate effect in a group of young (less than 24 years old) and middle aged (24 to 56 years old) women who are habitual wearers of high-heeled shoes, after wearing their shoes without heels and with an average heel of 8.7 cm. The results are indicative of a reduction in pelvic tilt and not of lordosis when using the shoe with the heel.

Objective of the study

The aim of this study is, given the remarkable heterogeneity of the data in the literature, to investigate whether artificial heel lift affects spinal posture and pelvic position in the sagittal plane in a group of healthy men and women. A better understanding of the immediate reaction of the spinal column in search of equilibrium during heel lifting could increase the knowledge useful for understanding low back pain associated with the use of shoes with heels and help preventing and/or treating it.

What is meant to prove

The aim of this study is to investigate whether artificial heel lift immediately influences spinal posture and pelvic position in the sagittal plane in a group of healthy male and female subjects not used to wear high-heeled shoes. The recent study by Schroeder and Hollander (2018) used a sample of female subjects with habitual heels; moreover, compared to the previous work, this research also includes the investigation at the level of dorsal kyphosis.

What is added to current knowledge

Given the extreme variability of the data reported in the literature, a better understanding of the adjustments of the immediate reaction of the spine and pelvis to heel elevation. These data could increase knowledge of the pathogenesis of low back pain related to heel height and help prevent or treat it.

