Primary outcome: investigate the immediate postural response of the pelvis, lumbar and dorsal spine in search of balance during the passive elevation of 3 cm and 7 cm of the heels with a non-invasive tool in non-users of high-heeled shoes.

Secondary outcome: investigate if there is a different response in the two sexes. Assuming that the reaction to heels can also be linked to the habit of wearing high-heeled shoes, use the response of a group of males, who are assumed to have never worn high-heeled shoes (7 cm) in their own life, can further clarify what type of response occurs in the search for immediate postural balance of the pelvis and the dorsal-lumbar spine after the raising of the heels.

Study design

Cross sectional study. Monocentric.

Duration of the study

Six months

Materials and methods

Setting: OSCE (Osteopathic Spine Center Education), osteopathic school based in Bologna.

Population: 100 students (50 females and 50 males) to be enrolled in OSCE school by making announcements during the lessons. The number of subjects to be evaluated was decided on the basis of the most recent work which used the same methodology, which evaluated a sample of 36 women (Schroeder and Hollander 2018). A similar number between males and females was set to improve the statistical comparison.

Following the ethical principles of the Declaration of Helsinki, a paper information will be provided where there will be an explanation of the intent and purpose of the study to all subjects prior to their participation; in addition, a paper consent will be provided, together with the information, on which to obtain the voluntary written informed consent.

Inclusion criteria: asymptomatic young subjects.

Exclusion criteria:

- structural or neurological anomalies that may prevent from maintaining an upright position for 5 sec. with their heels elevated on a 7 cm high basement;
- habitual users of shoes with 7 cm high heels, with a frequency of at least twice a week and / or less than 3 hours / week as proposed by a previous study (de Oliveira Pezzan et al. 2011);

- low back pain in the past 30 days.

Measurement method

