2. bare trunk with pants and briefs lowered to half of the glutei
3. in the case of long hair, it will be required to tie it with suitable means (cap, hair clips, hair bands, etc.) so that the neck is visible up to the hairline;
4. rings, watches and necklaces will be removed to avoid any interference with light lines (necklaces in particular increase this probability).

In the third survey, the heel will be raised by inserting a plastic bar symmetrically under both heels, as proposed in previous studies in which wood was used (Bendix et 1984; Franklin et al. 1995), by 3 cm; for the fourth evaluation it will be 7 cm.

After the first evaluation in the neutral position, before the evaluation with the heel lift, a second evaluation will be performed under the same conditions to evaluate the reproducibility of the data. The time between the two assessments will be less than 1 minute and the subject will not change position.

The spinometric analysis will be performed by specialized operators; the data will be entered after anonymization with an identification code on an Excel spreadsheet; the statistical analysis will be performed with the Prisma statistical program.

Statistic analysis

Descriptive analysis will be performed to determine mean values and standard deviations (SD).

It will be used:

- Kolmogorov-Smirnov test to verify the normal distribution;
- intra-class correlation coefficient test (ICC) and the t-test for paired data to evaluate the repeatability of the data between the first and second detection in neutral conditions;
- One-way ANOVA and paired t-test for data for comparison between neutral position, heels raised by 3 cm and 7 cm in both males and females;
- Cohen's d will be calculated for the difference between neutral conditions (NEU) and those with the rise (3-7cm) (d = 0.20 indicates a small effect size, d = 0.50 an effect size mean and d = 0.80 a large effect).
- t-test for independent data to evaluate if there are significant differences between the different positions (0-3 cm-7cm) between males and females.

Statistical significance will be accepted for p values <0.05.

Data analysis will be performed using Prism 8 software (Graphpad Software, S. Diego).

Bibliography

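### The paired t-test on the two neutral scans cannot show repeatability and the ICC has no units, so the plan states no measurement error in degrees or mm

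*Combined protocol and SAP*

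**What the plan says.** Each subject is scanned four times: twice barefoot in neutral, then with a 3 cm and a 7 cm rise (Evaluation Protocol). The purpose of the repeat is explicit: "a second evaluation will be performed under the same conditions to evaluate the reproducibility of the data". Its conditions are also given: "The time between the two assessments will be less than 1 minute and the subject will not change position".

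Statistic analysis names two tools for this repeat, an ICC whose form is not stated and "the t-test for paired data to evaluate the repeatability of the data between the first and second detection in neutral conditions". The general threshold is "Statistical significance will be accepted for p values <0.05". Means and SDs will be described. Heel effects are tested by one-way ANOVA and paired t-tests, and scaled by Cohen's d.

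On the device itself, the Introduction says that the reliability coefficients of the "rasterstereographic assessment method for the study of the sagittal plane were reported as excellent", with ICC above 0.95. It gives no error in degrees or millimetres. The six parameters listed under Investigated parameters are angles or distances in millimetres.

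No SEM, limits of agreement, minimal detectable change or acceptable error in units is planned.

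**The concern.** A paired t-test between two scans asks whether their means differ. It does not ask how close the two readings of one subject are. Random error sits in the denominator of the test statistic, so a larger error makes a given shift harder to detect. A non-significant result can mean that the scans agree, or that they are too noisy for the shift to show.

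The ICC does address random error, but only as a fraction of the total spread of readings. The same ICC corresponds to a small error in a homogeneous sample and a large one in a diverse sample. A reader who wants to know how many degrees of lordosis or millimetres of lumbar arrow the device can move by itself gets no direct answer from either statistic.

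What is at stake is the stated purpose of the second neutral scan. It could be reported as showing good repeatability on a p-value that does not bear on it, and the error in units that the scan could supply might not be reported at all.

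**Working it through.** **Inputs from the documents.** The sample is "100 students (50 females and 50 males) to be enrolled in OSCE school". Significance is at 0.05, taken as two-sided because sidedness is not stated. The literature ICC is above 0.95. There is no measurement-error figure in the plan to reproduce. The sample size rests on precedent and not on any effect, SD or power, so it supplies none either.

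**Assumptions.** The documents give no SDs. S, the SD of single readings across subjects, is taken as 3 to 10 units (degrees or mm). The simulation uses a true between-subject SD of 8 units.

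**1. Behaviour of the paired t-test.** Simulation of 20,000 data sets of n = 100, with the stated shift between scans 1 and 2. The half-width of the limits of agreement is 1.96 × √2 × SEM.

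| SEM | ICC | Limits of agreement | Rejects, no shift | Rejects, shift 0.5 |
|---|---|---|---|---|
| 0.5 | 0.996 | ±1.39 | 4.8% | 100% |
| 2 | 0.941 | ±5.54 | 4.9% | 41.6% |
| 8 | 0.50 | ±22.17 | 5.0% | 7.6% |

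With no shift, the rejection rate stays near 5% while the limits of agreement widen sixteenfold (22.17 / 1.39 = 15.9). With a fixed shift, rejection falls as noise rises.

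**2. Smallest shift that reaches significance.** The threshold is t(0.975, 99) / √100 = 1.984 / 10 = 0.198 SD of the differences. With SD of differences = S × √(2(1 − ICC)):
- ICC 0.95: 0.198 × √0.10 × S = 0.198 × 0.316 × S = 0.063 S
- ICC 0.50: 0.198 × √1 × S = 0.198 S

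The shift needed for significance is about three times larger for the much less reliable measurement.

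**3. What the ICC leaves open.** SEM = S × √(1 − ICC), and MDC95, the 95% minimal detectable change for one subject, = 1.96 × √2 × SEM. At ICC 0.95:
- S = 3: SEM = 3 × 0.2236 = 0.67; MDC95 = 1.86
- S = 6: SEM = 1.34; MDC95 = 3.72
- S = 10: SEM = 2.24; MDC95 = 6.20

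One ICC value thus covers more than a threefold range of error in units. Because the cited ICC is above 0.95, these are upper limits for each S if the study attains that level.

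**4. Effect on the group comparison.** Take S = 8 and ICC 0.95. The SD of differences from measurement error alone is 8 × √0.10 = 2.53. Its contribution to the standard error of a mean change is 2.53 / √100 = 0.25 for all subjects, or 2.53 / √50 = 0.36 within one sex. The single-reading SEM is 8 × 0.2236 = 1.79, about seven times the first figure. The SEM is therefore the wrong yardstick for a mean.

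**The case against.** The strongest reply is that the main analysis does not need a separate error figure. The question under Primary outcome concerns the response of a group, and the planned paired t-test of heel against neutral already carries random device error in the SD of its paired differences. That stands. A reader might infer that the trial cannot tell a heel effect from measurement error; for mean effects and random error, the plan does not support that inference.

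Three further replies have force.
- The plan never says that p>0.05 means repeatable or that p<0.05 means the opposite. It lists the ICC and the t-test together, and an ICC of 0.50 printed beside a non-significant p would expose gross noise.
- The t-test has a proper, limited use as a check for systematic shift. That matters because the neutral scans come first in the listed sequence, so drift would bear on the heel contrast.
- The SEM can be derived afterwards from the planned SD and ICC. In one simulated data set, both routes gave 1.69.

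These replies narrow the point but do not remove it. The plan assigns the t-test to repeatability, which it cannot assess. A mean difference with its CI is a better check for shift, because it shows how much drift remains compatible with the data. A derivable SEM is still not a planned one, and the derivation through the ICC depends on a form that is not stated.

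**Conclusion.** The point holds as a limited one. The paired t-test is the wrong instrument for repeatability, the ICC beside it gives no error in units, and the plan commits to no figure in degrees or millimetres. The data needed for a within-session figure are already collected; what is missing is the analysis.

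The direction of the t-test's behaviour does not depend on the assumed SD: for a fixed shift, more noise means fewer rejections. The sizes do depend on it. An SEM of 0.67 to 2.24 units at ICC 0.95 follows from S between 3 and 10.

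Two stronger conclusions should be avoided. The group comparison of heel heights is not undermined by this point. Nor should an individual MDC95 of several degrees be read as a hurdle for a mean change: with S = 8 and n = 100, the matching measurement-error bound for a mean is 1.96 × 0.253 = 0.50 units, against 4.96 for one subject.

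There is also a limit on the repeat itself. It is taken without a change of position, whereas the heel scans require a bar to be placed under both heels. Error estimated from it leaves out repositioning and may understate the error relevant to the heel comparison.

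**What to change.** In Statistic analysis, replace the paired t-test as the repeatability analysis with the following, for each of the six parameters:
- the mean difference between samples 1 and 2 with 95% CI, as the check for systematic shift
- Bland-Altman 95% limits of agreement
- SEM = SD of the differences / √2, in degrees or mm
- the ICC with its form stated (absolute agreement or consistency, single or average reading) and its 95% CI

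State that no conclusion on repeatability will be drawn from p>0.05.

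Report heel effects as mean change with 95% CI in degrees or mm, and do not judge group means against the single-reading SEM. If MDC95 = 1.96 × SD of the differences is reported, use it only to interpret individual changes. Say that it is a lower bound, because the repeat involved no repositioning; a share of subjects exceeding it could be inflated for the same reason.

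The cost is a few lines of text and a minor extra analysis of scans already planned.

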A three-dimensional posterior surface analysis is performed with the Formetric 4D® rasterstereographic device (Diers International GmbH, Schlangenbad, Germany). The device, already supplied at the Spine Center rehabilitation center in Bologna and made available free of charge for the study, is non-invasive and non-dangerous. The analysis of the spine curve with rasterstereography is performed with a purely optical modality.

[figure not shown]

fig. 1 - Scheme of the spinometric parameters to be recorded: pelvic inclination, lordotic angle, kyphotic angle.

[figure not shown]

fig. 2 - Scheme of the spinometric parameters to be recorded: cervical and dorsal arrow, anterior flexion of the trunk.

Investigated parameters

The data collected by the Formetric evaluation will be:

- 1) pelvic tilt angle (PI), the angle determined by the vertical and the tangent to lumbosacral junction (ILS);
- 2) ITL-ILS lordotic angle, measured between the tangents of the thoracolumbar junction (ITL) and the lumbosacral junction (ILS);
- 3) ICT-ITL kyphotic angle, measured between the tangents of the cervicothoracic junction (ICT) and the thoracolumbar junction (ITL); see fig. 1;
- 4) lumbar arrow (FL) horizontal distance in millimeters from the vertical line that passes through the kyphotic apex in the lumbar spine;
- 5) cervical arrow (FC) (horizontal distance in millimeters from the virtual vertical plumb line that passes through the kyphotic apex in the cervical spine);
- 6) antero-posterior flexion of the trunk (Trunk Inclination-TI) measured as the angle between the vertical line and the line passing through the prominent cervical vertebra (VP) to the line connecting the two dimples (DM); see fig. 2.

Participants will provide information on age, height and weight. A questionnaire will be administered to standardize the types of high-heeled shoes used and to verify their frequency of use.

Evaluation Protocol

- 1) sample 1: barefoot neutral position;
- 2) sample 2: barefoot neutral position;
- 3) sample 3: 3 cm rise under both heels;
- 4) sample 4: 7 cm rise under both heels.

The positioning with respect to the measurement system will be carried out according to the indications provided by the supplier.

To standardize the position subjects will be prepared for analysis as follows:

1. standing, back to the detection system, in a relaxed posture with the knees fully extended with bare feet on the floor (neutral position);

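### The overall test of neutral, 3 cm and 7 cm is named only as a one-way ANOVA, although every subject is measured in all three positions; it should be specified as repeated measures

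*Combined protocol and SAP*

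**What the plan says.** The Evaluation Protocol lists four recordings taken in sequence on each subject: two in neutral, then "sample 3: 3 cm rise under both heels" and "sample 4: 7 cm rise under both heels". The Population paragraph sets 50 females and 50 males.

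The Statistic analysis section compares the positions by "One-way ANOVA and paired t-test for data for comparison between neutral position, heels raised by 3 cm and 7 cm", and the sentence continues to both sexes ("7 cm in both males and females"). The other comparison tests in that list carry a label for the data structure. Repeatability uses a "t-test for paired data to evaluate the repeatability of the data", and the sex comparison uses a "t-test for independent data to evaluate if there are significant differences between the different positions". Cohen's d "will be calculated for the difference between neutral conditions (NEU) and those with the rise", with no standardiser given.

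The ANOVA alone has no such label. Repeated measures, a subject factor, a mixed model and a sphericity correction are not mentioned anywhere. The section also does not say which result decides if the ANOVA and the paired t-tests disagree.

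**The concern.** This bullet answers the primary outcome, the immediate response to a 3 cm and a 7 cm lift. An unqualified one-way ANOVA normally means the independent-groups test. Applied to three matched columns, it treats them as three separate groups of people and counts stable differences between subjects as noise. With positively correlated positions the error is conservative: it adds no false positives, but a real small shift can give a clearly non-significant overall p-value next to a significant paired t-test on the same data. Two analysts following this text in good faith could report opposite overall results.

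**Working it through.** **Inputs from the document.** Three positions per subject; 50 subjects per sex, 100 in total; significance at p < 0.05 (taken as two-sided for t-tests); benchmarks d = 0.20, 0.50 and 0.80. The plan has no power figure to reproduce: the sample size rests on a precedent of 36 women.

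**Assumptions.** The between-position correlation r is not given. The background section reports only same-measure reliability (ICC > 0.95), which is a different quantity, so r is varied from 0.5 to 0.95. Data are normal with equal variances and equal correlations. The shift d at 7 cm is in between-subject SD units. Profiles over (neutral, 3 cm, 7 cm) are linear (0, 3d/7, d) and two step forms, (0, 0, d) and (0, d, d).

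**Why the error term is wrong.** Let σ² be the total variance at one position. With no true shift:

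- expected mean square for position = σ²(1 − r)
- expected error mean square, independent groups = σ²
- expected error mean square, repeated measures = σ²(1 − r)

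The literal F therefore centres near 1 − r instead of 1. With df 2 and 147, P(F > x) = (1 + 2x/147)^(−73.5). Setting this to 0.05 gives a critical value of 3.06. At r = 0.5 the literal test needs 3.06/0.5 = 6.12 on the correct scale, and (1 + 12.24/147)^(−73.5) ≈ 0.003. This approximation agrees with the simulated 0.27% in the table.

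**Simulation, n = 50, linear profile, 20,000 trials per cell.** Each cell shows independent-groups ANOVA / repeated-measures ANOVA with Geisser-Greenhouse correction, as % rejecting.

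| r | no shift | 0.2 SD | 0.5 SD | 0.8 SD |
|---|---|---|---|---|
| 0.5 | 0.27 / 4.7 | 3.6 / 21.7 | 58.3 / 88.7 | 98.6 / 99.9 |
| 0.7 | 0.01 / 5.0 | 0.9 / 33.2 | 57.3 / 98.5 | 99.6 / 100 |
| 0.8 | 0 / 5.0 | 0.3 / 48.4 | 57.5 / 99.9 | 99.9 / 100 |
| 0.9 | 0 / 4.9 | 0 / 79.6 | 57.0 / 100 | 100 / 100 |
| 0.95 | 0 / 5.1 | 0 / 98.3 | 56.9 / 100 | 100 / 100 |

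Under the step profiles the ranges over r are 0–6% against 28–100% at 0.2 SD, and 76–91% against 96–100% at 0.5 SD.

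**The paired t-test, neutral against 7 cm.** The noncentrality is d√n / √(2(1 − r)). At d = 0.2 and r = 0.5 this is 0.2 × 7.071 / 1 = 1.41, power 28%. At r = 0.95 it is 0.2 × 7.071 / 0.316 = 4.47, power 99%. At d = 0.5 power is 93–100%.

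**How often the two results clash** (paired t-test significant, ANOVA not; range over r):

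| Shift | Independent groups | Repeated measures |
|---|---|---|
| 0.2 SD | 24–99% | 0–13% |
| 0.5 SD, linear | 35–43% | 0–5% |
| 0.5 SD, step | 9–20% | at most 1.4% |
| 0.8 SD, linear | at most 1.4% | under 0.1% |

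**Sexes pooled, n = 100.** At 0.2 SD, 0–17% against 41–100%. At 0.5 SD, 95–100% against 99.6–100%.

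**Dependence on the standardiser.** If d is scaled by the SD of the differences, a value d corresponds to d√(2(1 − r)) in the units above. At d = 0.8 and r = 0.95 that is 0.8 × 0.316 = 0.25 SD. Literal power at d = 0.8 (n = 50, linear) then falls from 99% at r = 0.5 to 0% at r = 0.95, against at least 99.9% for repeated measures.

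**The case against.** The strongest reply is that the fault exists under only one reading of translated text. The title page says the document is a translation, and the word order of the bullet is awkward. In the source, the word for paired may have covered both tests. A repeated-measures ANOVA with one factor is also a one-way ANOVA, so the label could be called incomplete rather than wrong. This stands as a caution, and the figures above apply only to the literal reading. It does not remove the gap, because the plan as it stands does not specify the matched version.

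Second, the paired t-tests are not conditional on the ANOVA, so the plan can still find the shift. That is correct and limits the harm to a misleading overall p-value. The paired tests are sound in their error term only. No multiplicity adjustment is stated, and three unadjusted pairs carry about a 12% chance of at least one false positive. That is a separate matter, but it gives a reader reason to look to the overall test.

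Third, some disagreement between an overall test and a pairwise test is normal. It is, but with the correct ANOVA it is at most 13% at 0.2 SD.

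Fourth, the correlation, profile and standardiser are all assumed, so the size of the loss is uncertain. That also stands. The conservative direction holds for any positive correlation.

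**Conclusion.** The point holds and should be fixed. The design is within-subject, and the only overall test of the primary comparison is named without the term that would make it fit that design. Followed literally, its p-value is too large. The distortion is severe for a 0.2 SD shift, moderate at 0.5 SD when the sexes are analysed separately, small at 0.5 SD when they are pooled, and negligible at 0.8 SD. These boundaries assume positive correlation of 0.5 to 0.95 between positions and shifts measured in between-subject SDs. They move if Cohen's d is scaled by the SD of the differences. Confidence is medium, because repeated measures may have been intended.

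**What to change.** In the Statistic analysis section, replace the one-way ANOVA by a repeated-measures one-way ANOVA with subject as the matching factor and Geisser-Greenhouse correction. Run it within each sex, which is the natural reading of the bullet. Keep the paired comparisons of neutral with 3 cm and neutral with 7 cm. The cost is one line of analysis wording, with no extra data or visits.

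### The primary question concerns one mixed group, but the only heel-height tests appear to be per sex (n=50 each), with no test on all 100 subjects and no sex-by-height interaction

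*Combined protocol and SAP*

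**What the plan says.** - **Objective of the study:** the question is whether heel lift "affects spinal posture and pelvic position in the sagittal plane in a group of healthy men and women".
- **Primary outcome:** the immediate postural response "during the passive elevation of 3 cm and 7 cm of the heels with a non-invasive tool in non-users of high-heeled shoes". It is not divided by sex.
- **Secondary outcome:** "Secondary outcome: investigate if there is a different response in the two sexes".
- **Population (Materials and methods):** "100 students (50 females and 50 males) to be enrolled in OSCE school". The number was "decided on the basis of the most recent work which used the same methodology, which evaluated a sample of 36 women". On the equal split: "A similar number between males and females was set to improve the statistical comparison".
- **Statistic analysis, heel height:** one-way ANOVA and paired t-test comparing the neutral position with "heels raised by 3 cm and 7 cm in both males and females".
- **Statistic analysis, other lines:** Cohen's d for neutral against each rise is listed without a split by sex. An independent-samples t-test compares males and females across the 0, 3 and 7 cm positions. Significance is p < 0.05, with sidedness not stated.

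No line names a test on all 100 subjects, a model with sex as a factor, or an interaction between sex and heel height.

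**The concern.** The primary question and the analysis that should answer it do not refer to the same set of subjects. If the heel-height tests are run within each sex, three things follow.

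1. Each primary test uses half the recruited sample, although every subject contributes to the primary question.
2. The primary result becomes a pair of p values, one for men and one for women, and the plan does not say what to conclude when they disagree.
3. Disagreement is easily read as a sex difference. A significant result in one sex and a non-significant one in the other is not evidence of a different response, and it can arise by chance when the response is the same.

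The plan does contain a direct between-sex test, but that test appears to compare the sexes at each position. Men and women may differ in lordosis or kyphosis when standing barefoot, and such a difference would carry over into the 3 cm and 7 cm comparisons even if heel elevation changed posture equally in both. So the secondary question, a different response to elevation, has no test that clearly addresses it.

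**Working it through.** **Inputs from the documents.** 50 females and 50 males; alpha 0.05; three heel heights (0, 3, 7 cm); six parameters.

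**Assumptions.** The test is two-sided. The documents give no planning effect, SD or power, so the sample size of 100 cannot be reproduced and effects are taken over a range. The effect is dz = mean change from neutral / SD of the change. The values 0.20, 0.50 and 0.80 are borrowed from the plan's scale for interpreting Cohen's d; 0.30 and 0.40 fill the gap.

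**Power of one paired t-test.** With T a noncentral t variable on n − 1 degrees of freedom and noncentrality dz × √n, power = P(|T| > t(0.975, n − 1)). The critical value is 2.010 for n = 50 and 1.984 for n = 100. At dz = 0.30 the noncentrality is 0.30 × √50 = 2.12 per sex and 0.30 × √100 = 3.00 pooled, giving power 0.548 and 0.844.

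**Discordance.** If both sexes have the same true dz, the two per-sex tests are independent with equal power p, and the chance that exactly one is significant is 2p(1 − p). At dz = 0.30: 2 × 0.548 × 0.452 = 0.495.

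| dz (same in both sexes) | Power per sex, n=50 | Power pooled, n=100 | Exactly one sex significant |
|---|---|---|---|
| 0.20 | 28% | 51% | 41% |
| 0.30 | 55% | 84% | 50% |
| 0.40 | 79% | 98% | 33% |
| 0.50 | 93% | 99.9% | 12% |
| 0.80 | about 100% | about 100% | about 0% |

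With no effect in either sex the discordance is 2 × 0.05 × 0.95 = 9.5%.

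**Detectable effect and precision.** The dz detectable with 80% power is 0.40 per sex and 0.28 pooled. The 95% CI half-width is t(0.975, n − 1)/√n, which is 0.28 SD of the change per sex and 0.20 pooled.

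**Number of comparisons.** Six parameters and two contrasts with neutral give 6 × 2 = 12 male–female pairs of tests. If every pair had dz 0.30, the expected number of discordant pairs would be 12 × 0.495 = 5.9. With no effect anywhere it would be 12 × 0.095 = 1.1. These expectations do not depend on correlation between parameters.

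**Sensitivity to the definition of d.** If d is standardised by the between-subject SD, with equal SDs at each height, then dz = d/√(2(1 − r)), where r is the unstated correlation between positions. For d = 0.20:

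| r | dz | Power n=50 | Power n=100 | Discordance |
|---|---|---|---|---|
| 0.5 | 0.20 | 28% | 51% | 41% |
| 0.8 | 0.32 | 59% | 88% | 48% |
| 0.9 | 0.45 | 87% | 99% | 22% |
| 0.95 | 0.63 | 99% | 100% | 1.5% |

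**Direct test of the secondary question.** A two-sample comparison of change from neutral, 50 against 50, has about 70% power for a standardised difference of 0.50. Its detectable difference at 80% power is (1.96 + 0.84) × √(2/50) = 0.56.

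**The case against.** **The text may not mean per sex.** It does not say separately or within each sex, the document is a translation, and the neighbouring Cohen's d line is not split. The phrase could simply mean that subjects of both sexes are included. This stands in part. A reader might infer that the plan commits the primary question to two half-size analyses; the documents make that likely but do not establish it. The gap remains on either reading. A one-way ANOVA has no place for sex, so the listed tests either ignore sex or split by it, and the plan does not say which.

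**The plan tests the sexes directly.** It lists an independent t-test and nowhere says that a sex difference will be inferred from discordant p values. This also stands: a reader might suppose that the plan relies on such an inference, and it does not. But the listed test appears to address levels rather than change, so it does not close the gap.

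**Discordance is not inevitable.** Correct. The 50% at dz 0.30 is essentially the maximum of 2p(1 − p). A reader might take chance discordance to be the expected outcome whatever the effect; it is common for small to moderate effects, 12% at dz 0.50 and negligible at 0.80. If measurements correlate strongly within subject, even a small between-subject d is well powered in each sex. Small effects cannot be set aside, however: the Introduction cites studies finding increased, reduced and unchanged lordosis.

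**Pooling can dilute.** With dz 0.50 in one sex and 0 in the other, the pooled contrast is 0.25, with about 67–70% power at n = 100, against 93% in the responding sex alone. The plan includes men because habit may alter the response, and 50 per sex exceeds the 36 women of the precedent study. Per-sex estimates are therefore legitimate. This is a reason to report them and the interaction beside the pooled result, not to leave the whole-group question without a whole-group test.

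**Conclusion.** The concern holds in a conditional form. What the documents show firmly is that the primary question is about one group, that no test on all 100 subjects is named, and that no listed line clearly tests a sex difference in the response to heel rise. On the more natural per-sex reading, the loss of power is about 23 percentage points at dz 0.20, 29 at 0.30, 19 at 0.40 and 6 at 0.50, and there is none to speak of at 0.80. Over the same values, spurious disagreement between the sexes runs from 50% at its highest to about 0%. The comparison assumes two-sided 0.05 tests, the same true effect in both sexes, and effect sizes that are ours and not the plan's. The data collected are adequate for a better analysis, so this is a change that should be made and not a flaw in the design.

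**What to change.** Replace the heel-height line in the Statistic analysis section with one repeated-measures model per parameter on all 100 subjects: heel height (0, 3, 7 cm) within subject, sex between subjects, and their interaction.

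- **Primary result:** the 3 cm and 7 cm contrasts with neutral, averaged over sex, with 95% CIs.
- **Secondary result:** the sex-by-height interaction, expressed as the male–female difference in change from neutral at 3 cm and at 7 cm, with 95% CIs. This takes the place of the position-by-position t-test as the answer to the secondary outcome.
- **Supportive:** per-sex changes with 95% CIs, without separate significance claims.

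The cost is a change of SAP wording. Subjects, measurements and schedule stay the same. The downside is that a response differing strongly by sex is diluted in the averaged contrast, so the plan should require the interaction and the per-sex estimates to be reported beside the primary result. With 50 per sex the interaction has limited power (about 70% for a standardised difference of 0.50), so a non-significant interaction should not be reported as showing that the sexes respond alike.
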